### **Amenorrhea**

The number and percentage of subjects who achieve amenorrhea will be calculated for each treatment group. The amenorrhea analysis includes subjects on study drug for at least 38 days. For each subject, amenorrhea at the Final Month is defined as having 0 days of bleeding or spotting during the last 28 days prior to and including the last dose day, with the interval starting at or beyond Study Day 11. If a subject does not have evaluable AH data during the last 28 days and no bleeding or spotting or "There was no visible blood on the sanitary products" is indicated on UBQ, then she is considered amenorrheic. The denominator will be the number of subjects with at least 38 days on study drug and having an amenorrhea status at the Final Month. The number and percentage of subjects with amenorrhea at Final Month will be summarized by treatment group and compared between the elagolix treatment group and placebo using the Miettinen-Nurminen (M-N) method.

Time to amenorrhea is defined as the number of days from the first study drug dose date to the day a subject achieves amenorrhea (i.e., the day a subject achieves amenorrhea – the first study drug dose date + 1). For a subject who achieves amenorrhea, the day she achieves amenorrhea is defined as the next day of the last bleeding/spotting day during the Treatment Period. The median, Q1, and Q3 of time to amenorrhea will be calculated for subjects who achieve amenorrhea using Kaplan-Meier method.

In the monthly analysis of bleeding for amenorrhea, the numerator will be the number of subjects on treatment who do not bleed or have spotting during the specified time window specified in [Table 1](#) (but may have begun bleeding or spotting thereafter) and the denominator will be the number of subjects on study drug for the full window and having an amenorrhea status for that month.

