**Table 1. Monthly Analysis of Bleeding for Amenorrhea**

Time Interval	Amenorrheic Status
Month 1 (Days 2 – 28)	Subject do not bleed or have spotting during Study Days 2 – 28 (Truncated, 27-day window)
Month 2 (Days 29 – 56)	Subject do not bleed or have spotting during Study Days 29 – 56
Month 3 (Days 57 – 84)	Subject do not bleed or have spotting during Study Days 57 – 84
Month 4 (Days 85 – 112)	Subject do not bleed or have spotting during Study Days 85 – 112
Month 5 (Days 113 – 140)	Subject do not bleed or have spotting during Study Days 113 – 140
Month 6 (Days 141 – 168)	Subject do not bleed or have spotting during Study Days 141 – 168
Final Month (last 28 days prior to and including the last dose day)	Subject do not bleed or have spotting during the last 28 days prior to and including the last dose day

Incidence and cumulative incidence of amenorrhea by last bleeding/spotting day at each month will be reported using the categories specified in [Table 2](#).

The summary will be provided including all subjects who have at least 38 days on study drug. If a subject meets the criteria for amenorrhea but discontinues, this subject's amenorrheic status will be carried forward to the time points after the subject has discontinued study drug. The denominator will be the number of subjects who have at least 38 days on study drug and have an amenorrhea status at Final Month.

Plots will be provided by treatment group for percentage of subjects with incidence and cumulative incidence of amenorrhea during the Treatment Period, respectively.

In all the analysis for amenorrhea above, if the observed MBL volume over a window (but treat "Subject only had spotting that did not require the use of sanitary products" on UBQ the same as bleeding) is 0 mL for a subject, then the subject is considered as no bleeding/spotting during that interval. Last bleeding/spotting day refers to the last day with observed AH data > 0 mL or the last day with UBQ indicating bleeding or spotting.

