**Table 2. Categorical Summary of Incidence and Cumulative Incidence of Amenorrhea**

Analysis	Time Interval	Numerator Calculation
Incidence	Month 2 (≤ Study Day 56)	Last bleeding/spotting day occurs during Study Days 1 – 28
	Month 3 (Study Day 57 – 84)	Last bleeding/spotting day occurs during Study Days 29 – 56
	Month 4 (Study Day 85 – 112)	Last bleeding/spotting day occurs during Study Days 57 – 84
	Month 5 (Study Day 113 – 140)	Last bleeding/spotting day occurs during Study Days 85 – 112
	Month 6 and after (Study Day ≥ 141)	Last bleeding/spotting day occurs after Study Day 113
Cumulative	Month 2 (≤ Study Day 56)	Last bleeding/spotting day occurs before Study Day 29
	Month 3 (Study Day 57 – 84)	Last bleeding/spotting day occurs before Study Day 57
	Month 4 (Study Day 85 – 112)	Last bleeding/spotting day occurs before Study Day 85
	Month 5 (Study Day 113 – 140)	Last bleeding/spotting day occurs before Study Day 113
	Month 6 and after (Study Day ≥ 141)	Last bleeding/spotting day occurs after Study Day 113

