### **Suppression of bleeding**

Suppression of bleeding is defined similarly to amenorrhea except that spotting is allowed. For each subject, achieving suppression of bleeding at the Final Month is defined as having 0 days of bleeding (spotting allowed) during the last 28 days prior to and including the last dose day with the interval starting at or beyond Study Day 11. The

suppression of bleeding analysis includes subjects with at least 38 days on study drug. If a subject does not have evaluable AH data during the last 28 days and no bleeding is indicated on UBQ ("Subject only had spotting that did not require the use of sanitary products" or "There was no visible blood on the sanitary products" is allowed), then the subject will be considered having achieved suppression of bleeding. The denominator will be the number of subjects with at least 38 days on study drug and having a suppression of bleeding status at the Final Month.

The number and percentage of subjects achieving suppression of bleeding at Final Month will be summarized by treatment group and compared between the elagolix treatment group and placebo using the Miettinen-Nurminen (M-N) method.

Time to suppression of bleeding is defined as the number of days from the first study drug dose date to the day a subject achieves suppression of bleeding (i.e., the day a subject achieves suppression of bleeding – the first study drug dose date + 1). For a subject who achieves suppression of bleeding, the day she achieves suppression of bleeding is defined as the next day of the last bleeding day during the Treatment Period. The median, Q1, and Q3 of time to suppression of bleeding will be calculated for subjects who achieve suppression of bleeding using Kaplan-Meier method.

Monthly analysis of bleeding for suppression of bleeding, incidence and cumulative incidence of suppression of bleeding will be provided in the same way as will be done for amenorrhea in [Table 1](#) and [Table 2](#). Plots will be provided by treatment group for percentage of subjects with incidence and cumulative incidence of suppression of bleeding during the Treatment Period, respectively.

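### SAP Table 2 assigns amenorrhea by the date of the last bleed alone, so women who fail the SAP's own 28-day definition can enter its numerators

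*SAP*

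**What the plan says.** SAP Section 8.4 (Amenorrhea) gives the definition: "amenorrhea at the Final Month is defined as having 0 days of bleeding or spotting during the last 28 days" up to and including the last dose day.

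Table 2 then sets the numerators for incidence and cumulative incidence:

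- Month 3 incidence: "Last bleeding/spotting day occurs during Study Days 29 – 56".
- Month 3 cumulative: "Last bleeding/spotting day occurs before Study Day 57".
- Month 6 and after, worded identically in the incidence and cumulative blocks: "Last bleeding/spotting day occurs after Study Day 113".

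The text between Tables 1 and 2 gives the denominator as the "number of subjects who have at least 38 days on study drug and have an amenorrhea status at Final Month". It also says that a woman who meets the amenorrhea criteria and then discontinues has that status carried forward to later time points. The last bleeding/spotting day is the last day with a positive alkaline hematin volume, or with bleeding or spotting on the Uterine Bleeding Questionnaire. No clear interval has to follow it.

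The Suppression of bleeding part of Section 8.4 extends this: "incidence and cumulative incidence of suppression of bleeding will be provided in the same way as will be done for amenorrhea".

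**The concern.** A last bleeding day is not the same as amenorrhea. A woman who stops drug a few days after a menses has a last bleeding day, but she has not had 28 clear days on drug. The numerator column does not separate her from a woman who truly stopped bleeding.

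Later data will not correct this, because Section 3.22 of the Operations Manual requires no product collection in follow-up. Such a stop is also an ordinary event: eligibility criterion 18 in protocol Section 5.1 requires cycles of 24 to 38 days, so women enter the study menstruating regularly.

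At stake are the incidence and cumulative summaries, and their plots by treatment group, for amenorrhea and for suppression of bleeding. A programmer who follows the column literally would show some women as achievers there who are non-achievers in the Final Month result.

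**Working it through.** **Inputs.** D is the last dose day and L the last bleeding/spotting day, with L no later than D. The definition, the 38-day minimum and the rows come from SAP Section 8.4 and Table 2.

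**Reproducing the SAP's own figure.** The Final Month runs from Day D − 27 to Day D. At the minimum exposure, D = 38, it starts on Day 38 − 27 = 11. This agrees with "with the interval starting at or beyond Study Day 11".

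**The definition in terms of D and L.** A woman is amenorrheic at the Final Month only if L ≤ D − 28. A Table 2 row conflicts with the definition when L falls in the row but L > D − 28.

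**Worked case, D = 60 and L = 52.**

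- Exposure is 60 days, above the 38-day minimum.
- The Final Month is Days 33 to 60. Day 52 lies inside it, so her status is no, with 60 − 52 = 8 clear days.
- Denominator: she is in it. Having an amenorrhea status must mean a known yes or no, because the same phrase defines the denominator of the Final Month percentage, which would otherwise always be 100%.
- Incidence: Day 52 lies in Days 29 to 56, so she meets the Month 3 criterion.
- Cumulative: Day 52 is before Days 57, 85 and 113, so she meets the Month 3, 4 and 5 criteria.

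**Where the Month 3 incidence row conflicts.** The conflicting values of L run from the larger of 29 and D − 27 to the smaller of 56 and D.

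| Last dose day D | Last bleeding days counted although status is no |
|---|---|
| 38 | 29 to 38 |
| 60 | 33 to 56 |
| 70 | 43 to 56 |
| 83 | 56 only |
| 84 or later | none |

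The conflict in this row is therefore possible only for last doses on Days 38 to 83.

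**Women treated to Day 168.** Amenorrhea requires L ≤ 168 − 28 = 140. The Month 2 to 5 rows stop at L = 112, so they never conflict. The Month 6 row takes L from 114 to 168, which is 168 − 114 + 1 = 55 possible days. Of these, Days 141 to 168 (28 days) fall inside the Final Month. A woman who last bled on Day 165 would be counted.

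**After the fix.** The woman in the worked case leaves every numerator and stays in the denominator. For a woman treated to Day 168, the Month 6 incidence row keeps only L = 114 to 140.

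**The case against.** The strongest reply is that Section 8.4, read as a whole, treats Table 2 as a timing breakdown for women who achieve amenorrhea. The carry-forward sentence applies only to a woman who meets the criteria. Time to amenorrhea is likewise dated from the last bleed only for women who achieve it. On that reading, the woman in the worked case has no status to carry into Months 4 and 5.

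This probably shows what was intended, and it argues against counting her after she stopped. It does not settle the matter. The sentence governs carry-forward only, does not take her out of the Month 3 rows, and is absent from the numerator column. Where the SAP wanted such a condition it wrote one: time to amenorrhea is restricted to achievers, and the monthly analysis requires the full window on drug.

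Three stronger readings are tempting, and the documents do not support them:

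- **A reader might infer that Table 2 sweeps in every menstruating woman.** For women treated to Day 168 the Month 2 to 5 rows imply a clear Final Month, so regular menstruators who complete can enter only at Month 6. A woman with no bleeding on treatment has no last bleeding day to classify.
- **A reader might size the error from SAP Appendix D**, taking the shortfall from 32:16 randomized to 28:14 as 4 and 2 false achievers. Those figures are an assumed share with observed primary endpoint data, not a discontinuation rate. An early stopper's Final Month is anchored to her last dose, so she may well be among the observed. Women without Final Month data will often lack a status and leave the denominator.
- **A reader might infer that the arm with more dropout will look better.** That would need unequal early stopping among women still menstruating, and no figure in the documents bears on it.

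**Conclusion.** The point stands as a gap between the Table 2 numerators and the definition they are meant to summarize. Taken literally, the column counts some discontinuers who were still menstruating and, through the Month 6 row, some women who bled in their last 28 days of full treatment. The same gap carries over to suppression of bleeding.

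Its reach is limited. These are descriptive summaries and plots of additional endpoints, in a study that the protocol's summary of changes calls exploratory. The primary endpoint, the Final Month comparisons of amenorrhea and suppression, and the monthly analysis in Table 1 are unaffected. The size in this trial cannot be computed, because the documents give neither the timing of discontinuations nor bleeding-day data.

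The conclusion rests on two readings: that an amenorrhea status means a known yes or no, and that the numerator column is applied as written.

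**What to change.** Add one condition to every Table 2 numerator, for example: *and the subject meets the Final Month amenorrhea (or suppression of bleeding) definition in Section 8.4*. State that women with a known status who do not meet it remain in the denominator as non-achievers in all rows.

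The Month 6 rows need a separate correction. The cumulative row repeats the incidence wording and so is not cumulative, and a last bleed on Day 113 falls in no row of either block.

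The added condition costs one sentence in the SAP and one condition in the program; the Month 6 correction is a small edit to the table. No new data are needed.

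### SAP Table 2: the Month 6 cumulative row repeats the incidence rule, so it accumulates nothing, and a last bleed on Study Day 113 falls in no row

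*SAP*

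**What the plan says.** Table 2 in SAP Section 8.4 has an incidence block and a cumulative block, each running from Month 2 to Month 6 and after.

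- The incidence rows for Months 2 to 5 use consecutive 28-day windows for the last bleeding or spotting day, beginning with "Last bleeding/spotting day occurs during Study Days 1 – 28" and ending with Days 85 to 112.
- The cumulative rows for Months 2 to 5 use upper limits only. The Month 5 row is "Last bleeding/spotting day occurs before Study Day 113".
- The Month 6 row is the same in both blocks: "Last bleeding/spotting day occurs after Study Day 113".

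The text introducing Table 2 sets one denominator for the summary: the "number of subjects who have at least 38 days on study drug and have an amenorrhea status at Final Month". It also says that when a woman meets the amenorrhea criteria and then discontinues, her "amenorrheic status will be carried forward to the time points after the subject has discontinued study drug". The Final Month amenorrhea proportion, defined earlier in Section 8.4, has the same denominator, the "number of subjects with at least 38 days on study drug and having an amenorrhea status at the Final Month".

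The table feeds figures: "Plots will be provided by treatment group for percentage of subjects with incidence and cumulative incidence of amenorrhea during the Treatment Period". It is also reused for a second endpoint: "Monthly analysis of bleeding for suppression of bleeding, incidence and cumulative incidence of suppression of bleeding will be provided in the same way" as for amenorrhea.

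**The concern.** With a fixed denominator and status carried forward, a cumulative incidence can only rise or stay level. The Month 6 cumulative rule breaks this by reversing direction, from an upper limit to a lower limit. Four problems follow.

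1. Every woman counted by Month 5 leaves the count at Month 6, so the curve can fall at its last point.
2. The carry-forward rule cannot operate. A woman who achieves amenorrhea and stops drug early has an early last bleed, which the Month 6 row excludes.
3. The end-of-treatment cumulative value will disagree with the Final Month proportion in the same section, unless nobody achieved amenorrhea with a last bleed on or before Day 113.
4. Day 113 lies between the Month 5 rows, which end at Day 112, and the Month 6 rows, which begin at Day 114.

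Two gaps lie alongside these. Table 2 does not say that its numerators are limited to women who meet the Final Month amenorrhea definition, although the surrounding text implies it. It also gives no incidence row to a woman with no bleeding day on treatment.

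At stake is the last point of the cumulative table and plot, for amenorrhea and for suppression of bleeding.

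**Working it through.** **Row coverage.** Each possible last bleeding day from 1 to 174 (Day 168 plus the 6-day late window for the Month 6 visit, Operations Manual Section 2.2) was tested against each row as written.

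| Row | Incidence covers | Cumulative covers | Running union of incidence rows |
|---|---|---|---|
| Month 2 | 1–28 | up to 28 | 1–28 |
| Month 3 | 29–56 | up to 56 | 1–56 |
| Month 4 | 57–84 | up to 84 | 1–84 |
| Month 5 | 85–112 | up to 112 | 1–112 |
| Month 6 and after | 114 onward | 114 onward | 1–112 and 114 onward |

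For Months 2 to 5 the cumulative row equals the running union. At Month 6 it omits Days 1 to 112. Day 113 is the only day in no incidence row and the only day in no cumulative row. The Month 5 and Month 6 cumulative sets have no day in common.

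**Effect on women who stop early.** Let L be the last dose day. Final Month amenorrhea requires no bleeding or spotting on Days L − 27 to L, so the last bleed is no later than L − 28.

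- L = 141: last bleed by Day 113, so she cannot be counted at Month 6.
- L = 142: last bleed by Day 114, the first case that can be counted.
- L = 168: only last bleeds on Days 114 to 140 are counted.

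No amenorrheic woman whose last dose is on or before Day 141 can appear in the Month 6 cumulative row, although her status is meant to be carried there.

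**Size.** With numerators limited to amenorrheic women, the shortfall at Month 6 is the Month 5 cumulative count plus any Day 113 cases. The documents give no expected amenorrhea counts, so those below are assumed, with no Day 113 cases. Denominators are the planned 32 and 16, which are the largest possible.

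| Case | Elagolix: by Month 5 / new at Month 6 | Placebo: by Month 5 / new at Month 6 | Elagolix at Month 5 | Month 6 as written, elagolix vs placebo | Month 6 correct, elagolix vs placebo |
|---|---|---|---|---|---|
| Low | 3 / 1 | 0 / 0 | 3/32 = 9.4% | 1/32 = 3.1% vs 0% | 4/32 = 12.5% vs 0% |
| Middle | 6 / 2 | 1 / 0 | 6/32 = 18.8% | 2/32 = 6.3% vs 0% | 8/32 = 25.0% vs 1/16 = 6.3% |
| High | 10 / 3 | 1 / 1 | 10/32 = 31.3% | 3/32 = 9.4% vs 1/16 = 6.3% | 13/32 = 40.6% vs 2/16 = 12.5% |

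The elagolix series falls from Month 5 to Month 6 in all three cases because each assumes more early than late achievers. In general it falls when fewer counted last bleeds lie after Day 113 than before it.

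**Without the restriction to amenorrheic women.** The Month 6 rule has no upper limit, so read literally it also counts women still bleeding at the end of treatment. Take 28 women with assumed counts of 5, 5, 4, 4 and 10 across the incidence rows. The cumulative series reads 17.9%, 35.7%, 50.0%, 64.3% and then 10/28 = 35.7%. With counts of 2, 2, 2, 2 and 20 it moves from 8/28 = 28.6% to 20/28 = 71.4%. In both, the last value is simply the incidence value.

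**The case against.** The best defence is that the intent is plain and little depends on the table. The block is labelled cumulative, four consistent rows come before the faulty one, and a falling curve would probably be noticed in programming checks. The listed endpoints are amenorrhea and suppression at the Final Month and at each month, and these are delivered by the Final Month comparison and Table 1. Table 2 carries no test, in a study that the protocol's summary of changes calls exploratory. This fairly limits the weight of the point. It does not remove it, because the SAP is the specification. Programmers left to repair the row could choose different cut-offs, such as Day 140 or all achievers.

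Three objections to the size also have force.

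- The direction depends on the numerator. The value is too low for amenorrheic women, but on a literal reading that includes women still bleeding it could exceed the true proportion. Even then the row falls short of its own running union by the Month 5 count plus Day 113 cases.
- The counts are illustrative, so a fall is possible but not certain.
- The true denominators may be below 32 and 16. Using the 28 and 14 that Appendix D assumes for observed primary data, the middle case becomes 2/28 = 7.1% vs 0% as written, against 8/28 = 28.6% vs 1/14 = 7.1%. The conclusion is unchanged.

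Finally, no passage requires the Month 6 cumulative value to equal the Final Month proportion. That is an inference from the shared denominator and the carry-forward rule.

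**Conclusion.** The point holds. The Month 6 cumulative row is wrong as written, Day 113 is uncovered in both blocks, and nothing elsewhere in the SAP corrects either. These conclusions follow from the table alone and need no assumed data.

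The size rests on two assumptions: that numerators are limited to women meeting the Final Month definition, and the illustrative counts. On these, the elagolix value at Month 6 is understated by 9.4 to 31.3 percentage points (3/32 to 10/32) and the placebo value by 0 to 6.3 points (0/16 to 1/16).

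The damage is confined to the descriptive incidence tables and plots for amenorrhea and suppression of bleeding. The primary endpoint, the Miettinen-Nurminen comparisons at the Final Month and the monthly analysis in Table 1 stand. The correction should be made, but it does not threaten the trial's main conclusion.

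**What to change.** Amend Table 2 as follows.

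1. Month 6 incidence: last bleeding or spotting day on or after Study Day 113.
2. Month 6 cumulative: all women meeting the Final Month definition, whatever their last bleeding day. This equals Month 5 cumulative plus Month 6 incidence. Count women with no on-treatment bleeding day in the Month 2 rows; otherwise they have no incidence row and the sum fails.
3. State in the table that every numerator is limited to women meeting the Final Month definition.

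Make the same edits for suppression of bleeding, using its own definition and last bleeding day.

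Extending the 28-day pattern instead (incidence Days 113 to 140, cumulative before Day 141) covers Days 1 to 140 without gaps. It would miss late achievers dosed beyond Day 168: a last dose on Day 174 allows a last bleed up to 174 − 28 = Day 146. The sponsor should confirm the cut-off, but the all-achievers rule avoids this problem.

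As a programming check, the Month 6 cumulative percentage must equal the Final Month percentage in each arm. The cost is an edit to one SAP table and its programming specification, with no new data.
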